## Study Packet is Opened

6. The study packet is opened in the presence of the study participant and contents of the folder are reviewed **Contents of Study Packets**:
  - a. Left pocket:
    - i. Aroma inhaler
    - ii. Welcome letter
    - iii. Consent form x 2
    - iv. Pre-Surveys (Comfort, Ease, and Stress)

- b. Right pocket:
  - i. Logbook
  - ii. Reminder paper (To post as a reminder) ADD DATES
  - iii. Closed postage paid envelope

7. Consent form is reviewed and signed

8. Pre-surveys for Comfort, Ease, and Stress are completed

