## Contents of Study Packets

1. Aroma inhaler
2. Aethereo®Stick Information Sheet
3. Cover letter (Appendix C)
4. Consent forms (2 copies)
5. Pre surveys (Comfort, Ease, and Stress)
6. Logbooks for Intervention or Control Groups (Appendix D)
7. Reminder paper (Appendix E)
8. 6 x 9 Postage paid return envelope
  - a. Post surveys (Comfort, Ease, Stress, Post Aroma)

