## Prior to opening a Study Packet

1. In a private location, Enroller will determine eligibility for this study.
  - a. Inclusion criteria are as follows:
    - i. Older than 18 years of age
    - ii. Currently enrolled in treatment
    - iii. Have completed intensive phase 1 and wish to continue with treatment
    - iv. Alert & oriented
    - v. Able to provide written consent
    - vi. Able to read & write English
  - b. Exclusion criteria are as follows:
    - i. Diagnosed with severe mental illness
    - ii. Medical history of asthma
    - iii. Other serious respiratory disease
    - iv. Known allergy to citrus
2. In a private location, Enroller will prescreen using created survey tool (appendix A)
  - a. Use the prescreening survey provided
  - b. Read prescreening survey to participants and record answers
  - c. If not contraindicated by prescreening questions, allow participant to smell the aroma inhaler (3 inches from nose)
    - i. Record all reactions, “liked the smell”, “sneezed”, “said ‘yuck’” on the presurvey. Record “no negative reactions” as applicable (This is a vital component of aromatic research)
3. IF PARTICIPANT IS INELIGIBLE, thank them for their time, note on MLS that they were screened and why they were ineligible. Use the special section at the end of the MLS to make this notation. Do not use an Id # space. Write “ineligible” and the date across the top of the survey.
4. IF PARTICIPANT IS ELIGIBLE, file prescreening form in predetermined place and obtain a study packet in the order they are arranged (001-098)
  - a. Enter date and name of participant on the **Random Number Table (RNT)** sheet
5. Record Unique Identifier packet number on **Master Log Sheet (MLS)**
  - a. Use MLS to track Participants
  - b. This Unique Identifier number is already on every document in each packet

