**AROMA INHALER STUDY**

**LOGBOOK**

**INTERVENTION GROUP**

**Directions for using your aroma inhaler and this logbook:**

**Follow these steps to use your aroma inhaler:**

1. Hold the aroma inhaler by the base
2. Twist off the cap. The inner part of the aroma inhaler with the essential oil-soaked cotton wick is part of a closed system and is not intended to be opened. All you need to do is twist off the cap
3. Hold the aroma inhaler within 3 inches of your nose
4. Breath in gently through your nose for 3 seconds
5. Hold your breath for about three seconds and then exhale gently through your mouth
6. Repeat this 3 times\* and then replace the cap and store your aroma inhaler in a cool, dry place away from children or pets. (You may repeat this breathing cycle more than 3 times each day, please remember to make a note of this in the comments section about when and why you did)
7. Use at least 3 times a day, and if you want to, use it more, but this should be recorded on the daily logbook page

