**AROMA INHALER STUDY**

**LOGBOOK**

**CONTROL GROUP**

**Follow these steps to use your Logbook:**

**Use your logbook to track your comfort on each of the seven days of the study**

Day 1

One time each day place an X on the line under "I feel as comfortable as possible today"

I feel as comfortable as possible today

Strongly disagree	Strongly agree
<hr/>	

Comments:

If you have any questions or comments, contact [name] at [[contact]](mailto:[contact]).

Thank you

Day 2

One time each day place an X on the line under "I feel as comfortable as possible today"

I feel as comfortable as possible today

Strongly disagree	Strongly agree
<hr/>	

Comments:

If you have any questions or comments, contact [name] at [[contact]](mailto:[contact]).

Thank you

Day 3

One time each day place an X on the line under "I feel as comfortable as possible today"

I feel as comfortable as possible today

Strongly disagree	Strongly agree
<hr/>	

Comments:

If you have any questions or comments, contact [name] at [[contact]](mailto:[contact]).

Thank you

Day 4

One time each day place an X on the line under "I feel as comfortable as possible today"

I feel as comfortable as possible today

Strongly disagree	Strongly agree
<hr/>	

Comments:

If you have any questions or comments, contact [name] at [[contact]](mailto:[contact]).

Thank you

Day 5

One time each day place an X on the line under "I feel as comfortable as possible today"

I feel as comfortable as possible today

Strongly disagree	Strongly agree
<hr/>	

Comments:

If you have any questions or comments, contact [name] at [[contact]](mailto:[contact]).

Thank you

Day 6

One time each day place an X on the line under "I feel as comfortable as possible today"

I feel as comfortable as possible today

Strongly disagree	Strongly agree
<hr/>	

Comments:

If you have any questions or comments, contact [name] at [[contact]](mailto:[contact]).

Thank you

Day 7

One time each day place an X on the line under "I feel as comfortable as possible today"

I feel as comfortable as possible today

Strongly disagree	Strongly agree
<hr/>	

Comments:

If you have any questions or comments, contact [name] at [[contact]](mailto:[contact]).

Thank you

- Thank you for completing your logbook for the seven-day aroma inhaler study!
- Please place your survey and logbook in the envelope provided and seal it
- **Return this envelope to the Chestnut Ridge Center within 3 days of completion**

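### The enrolment steps in the protocol body open a packet with an arm-titled logbook before consent and baseline; later amendments suggest the reverse order, but no available text requires it

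*Combined protocol and SAP*

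**What the plan says.** **Step list in the body.** Under Prior to opening a Study Packet, the enroller of an eligible person is told to "obtain a study packet in the order they are arranged (001-098"), and the person's name goes on the Random Number Table sheet. Step 5 adds that "This Unique Identifier number is already on every document in each packet". Under Study Packet is Opened, step 6 reads "The study packet is opened in the presence of the study participant and contents of the folder are reviewed", and the contents it lists include the logbook. Step 7 is "Consent form is reviewed and signed" and step 8 is "Pre-surveys for Comfort, Ease, and Stress are completed". Inhaler review and logbook dating come after that.

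**What the packet reveals.** Contents of Study Packets lists "Logbooks for Intervention or Control Groups (Appendix D"). In Appendix D one logbook is titled "INTERVENTION GROUP" and the other "CONTROL GROUP". Packets for both arms contain an inhaler when opened, so the logbook is the item that discloses the arm.

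**Timing table (Study Time Involved for Participants).** The packet is opened in step 2, ahead of the consent decision. The inhaler is tried in 2a, the logbook is gone through with the participant in 2b, and the pre-surveys come last, in step 3.

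**Later changes.** Updates to Study Protocol records online consent, a move to RedCap for all surveys, and the end of consent copies in mailed packets. The amendment in Appendix G puts the pre-surveys online, listed among changes tied to a Zoom meeting. It replaces in-person enrolment with mailing and adds a further contact once the materials arrive. It also moves the sniff of the inhaler, which it treats as part of the first prescreening, to the participant's home.

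**The concern.** If the body steps are followed, the arm can be known at two points where it should not be.

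- **At consent.** The packet is assigned, and the name entered on the randomisation sheet, before the person has agreed to take part. Someone who sees a control logbook may decline for that reason. Refusal that depends on arm makes the groups differ before treatment. It also affects the enrolment and retention rates that Aim 2 reports. The available text says how to log an ineligible person but gives no rule for an eligible person who declines after the packet is opened.
- **At baseline.** All three outcomes are self-reported, and the baseline enters the pre/post analysis. A baseline coloured by knowledge of the arm can appear as an effect or hide one.

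The amendments point to a better order, but the operating steps that staff would follow still describe the old one.

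**Working it through.** **1. The passages side by side**

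| Event | Step list in the body | Timing table | Amendments |
|---|---|---|---|
| Packet assigned | Steps 4-5 | Not shown | Not stated |
| Packet opened, contents seen | Step 6 | Step 2 | On arrival by mail |
| Consent | Step 7 | Step 2, after opening | Online; order not stated |
| Logbook gone over or dated | Step 11 | Step 2b | Not stated |
| Pre-surveys | Step 8 | Step 3 | Online, listed under a Zoom meeting |

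The step list and the timing table agree on packet, then consent, then pre-surveys. They conflict on the logbook: the table has it discussed before the pre-surveys, while the step list has it dated afterwards. Under the table, exposure to the arm before baseline is more direct.

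The amendments imply that consent and pre-surveys precede the packet, because there is an earlier Zoom meeting and a separate contact after the mail arrives. Two things prevent that from being settled. A home sniff that counts as first prescreening needs an inhaler already delivered. And no available passage says that consent or baseline must be complete before mailing or opening. The body also still places consent forms and pre-surveys in the packet. It keeps the control inhaler in a secure location, which does not fit a sniff at home.

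**2. The plan's own sample size**

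Inputs from Sample Size: f = 0.25, alpha 0.05, power 80%, two groups, m = 2 measurements, rho = 0.50.

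- Between-groups test: lambda = f²·N·m / (1 + (m−1)·rho) = 0.0625 × 98 × 2 / 1.5 = 8.17, with 1 and 96 df. Power is 0.808, so 98 is reproduced.
- Group-by-time test: lambda = f²·N·m / (1 − rho). This reaches 80% power at N = 34 (lambda 8.5, power 0.807).

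The stated 98 therefore matches the between-groups test. The Statistical Analysis Plan does not name the effect to be tested, so both are shown below.

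**3. Illustration of what an arm-dependent baseline could do**

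Every shift here is assumed; the documents give none. Take no true effect, 49 per arm, SD 1 at each time, rho 0.5, two-sided 5%, 96 df and a noncentral t. Let b be the arm difference induced at baseline and f the one induced at follow-up, in SD units.

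- SE factor = sqrt(2/49) = 0.202
- SD of change = sqrt(2 × (1 − 0.5)) = 1, so the group-by-time noncentrality is |f − b| / 0.202
- SD of the two-time mean = sqrt((1 + 0.5)/2) = 0.866, so the between-groups noncentrality is (|f + b|/2) / (0.866 × 0.202)

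For b = 0.2, f = 0: group-by-time 0.2/0.202 = 0.99, type I error 16.5%; between-groups 0.1/0.175 = 0.57, type I error 8.7%. The fix sets b = 0 and leaves f as it is.

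| b, f (SD) | Before fix: between-groups / group-by-time | After fix: between-groups / group-by-time |
|---|---|---|
| 0.1, 0 | 5.9% / 7.8% | 5.0% / 5.0% |
| 0.2, 0 | 8.7% / 16.5% | 5.0% / 5.0% |
| 0.3, 0 | 13.6% / 31.2% | 5.0% / 5.0% |
| 0.2, 0.1 | 13.6% / 7.8% | 5.9% / 7.8% |
| 0.2, 0.2 | 20.5% / 5.0% | 8.7% / 16.5% |

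In the last two rows the follow-up shift is in the same direction as the baseline shift. Group-by-time error is then unchanged or higher after the fix, because the two shifts had partly or wholly cancelled. What remains is the follow-up bias of an open trial. Arm-dependent refusal is not quantified, because the documents give no rate.

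**The case against.** **The in-person steps have been superseded.** Mailing replaced in-person enrolment, and consent and surveys went online. On this view only an outdated manual remains. That lowers the weight of the point but does not remove it: the current body still instructs staff in the old order, and the available amendment text does not state the new one.

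**The order may be stated elsewhere.** The consent form and Appendix H were not available for this review and may settle it. That is a fair limit. The point is that the visible passages do not require the order and conflict with one another, not that the plan lacks it everywhere.

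**The effect may be small.** The Ease measure asks about everyday life in general and the stress survey about the past week; only the comfort survey asks about the present moment. Both arms receive the $20 card, and controls receive the inhaler on completion, which weakens the motive to refuse. This stands, and is one reason not to treat 0.2 SD as an estimate.

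**Stronger readings that a reader might infer, and that the documents do not support:**

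- *That participants were in fact enrolled knowing their arm, or that results are biased.* The text shows the opportunity only.
- *That people are excluded, with the arm known, because they dislike the study sniff.* The Prescreen Survey item on dislike asks about earlier experience with bergamot. The sniff instructions only have reactions recorded, and ineligibility is tied to questions 1 and 2.
- *That the true type I error is 16.5%.* That figure rests on an assumed shift, confined to baseline, and on the group-by-time test, which is not the one that reproduces 98.

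**Conclusion.** The point holds as a conflict in the current text with a plausible route to bias. The body assigns and opens an arm-revealing packet before consent and baseline. The amendments suggest the reverse without requiring it, and the timing table and step list disagree on when the logbook is discussed. This is more than missing detail, because following the steps as written lets both refusal and baseline depend on arm.

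The size is not known from the documents. The type I error figures rest on assumed shifts, equal SDs and the plan's correlation of 0.5, and they show only that a modest baseline difference would matter at 49 per arm. Correcting the order removes the baseline part and leaves open-label bias at follow-up. For an open pilot this is minor to should-fix: a cheap improvement. If the consent form or Appendix H already fixes the order, what remains is aligning the body.

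**What to change.** - Rewrite the timing table and the sections from Contents of Study Packets to Documents to Leave in Participant Packet so that they match the Appendix G amendment and each other.
- State in one sentence that the eligibility questions, consent and the three pre-surveys are completed before a packet is assigned, mailed or opened.
- If the online pre-surveys are keyed to the packet number, use a screening ID and link it to the packet number after baseline.
- Count everyone assigned a packet as randomised to that arm, do not reuse the number, and report by arm anyone who leaves after assignment.
- Reconcile the control-arm instruction on where the inhaler is kept with the home sniff, and say where the sniff falls in the sequence.

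The cost is a short amendment, rewritten enrolment steps and possibly one ID field. The drawback is that, with mailing, the baseline will be some days old when day 1 begins, though in both arms alike.

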**Use of the Aethereo®Stick is reviewed (Appendix B for details about inhaler):**

- a. Enroller will either open or have participant open the sealed package for the Aethereo®Stick (aroma inhaler) open the outer sealed package
- b. Save the package for storage
- c. Pick up the inhaler and twist to the right to remove the cap
- d. There is no need to shake the inhaler
- e. Breath out gently
- f. While holding the inhaler about 3 inches (7.62 cm) from the nose
- g. Inhale through the nose using 3 sniffs as directed
- h. Hold breath for about 3 seconds
- i. Exhale for 3 seconds
- j. Repeat 3 times and then recap and store the inhaler in a safe place away from high heat and direct sunlight, children, and pets.
- k. NOTE: The Enroller will record all reactions to participant exposure to the aroma inhaler. Verbatim recording of any negative or positive response is vital. This is recorded on the Prescreening survey at the bottom of the form. Any negative or adverse reaction must be recorded. If no negative reaction, then the Enroller must write, "No negative reaction"

9. As needed use:

- a. The inhaler may be used more than 3 x daily
- b. Participants may use as needed and are asked to record all uses and reasons for uses in the provided logbook

10. Use other than instructed:

- a. If the participant uses the inhaler in some other fashion than instructed, they are asked to record this information as well (i.e. inhales x 10, inserts into nostril [which is considered safe], uses a different count to exhale etc.)

11. How Participant begins intervention:

- a. The participant begins the 7-day intervention at the beginning of their next full day of life (This allows for those who work nights etc.)
  - i. ADD DATES: Participants (preferable to have participants do this and not the Enroller) will add dates to pages of the logbook (e.g., If they received their packet and instructions on October 11, then they should begin their study on the NEXT FULL DAY, October 12, and their study would be

complete on October 18. Dates on pages should reflect the 7-days of the study, 10/12, 10/13 and so forth to 10/18)

- b. Three times daily means spaced out in 3 times, which could mean morning, afternoon, and evening, or anything else that is separated by approximately 4-6 hours (while awake)
- c. On day 1, 2, & 3 a text or email messages will be provided to participants to remind them to complete their diary indicating if they used the inhaler and mark how they are feeling on the VAS. They will be instructed to contact the researcher with any questions.
- d. Days 4, 5, 6, & 7, participants will not receive reminders.
  - i. A reminder will be sent on day 7.
  - ii. After day 7, all participants will open their final survey packet included in the folder.
  - iii. They will be instructed to complete the survey packet and return it and the logbook using the prepaid postage envelope.

## Documents to Leave in Participant Packet:

### INTERVENTION:

- iv. Those randomized to the Intervention group
  1. Left pocket (in this order)
    - a. Aroma inhaler
    - b. Aethereo®Stick information sheet
    - c. Welcome letter
    - d. Copy of consent
  2. Right pocket (in this order)
    - a. Logbook (with dates written in)
    - b. Reminder paper
    - c. Postage paid envelope (with date and instructions for return on note attached to front of the envelop)

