## Benefits

The participant may or may not directly benefit from participating in this research. The knowledge gained from this study may eventually benefit others.

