### CONTROL:

- v. Those randomized to the Control group (The AROMA INHALER from Control group packets is labeled with participants ID# and kept in a secure location until they complete the study. It will have been opened and demonstrated with the participant during study introduction)
  1. Left pocket (in this order)
    - a. Welcome letter
    - b. Copy of consent
  2. Right pocket (in this order)
    - a. Logbook (with dates written in)
    - b. Reminder paper
  3. Postage paid envelope (with date and instructions for return on note attached to front of the envelope)

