## AETHEROSTICK INFORMATION SHEET

## Aethereo®Sticks are a simple, portable, economical and effective way to enjoy the aromatherapeutic benefits of essential oils - wherever you are.

Long-lasting and safe for all ages, AethereoSticks are enjoyed by people at home, at work or school, and while traveling. AethereoSticks are widely used in hospitals for adjunctive symptom management and general well-being. Providing single-person exposure, they offer the ultimate in personal, private diffusion.

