### What is in an AethereoStick?

AethereoSticks are available in a wide range of undiluted essential oils and scientifically formulated essential oil blends. These precious plant materials can help with symptom relief and help to create a healing environment, which supports our natural abilities to balance, restore, and maintain overall wellness.

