**Follow these steps to use your Logbook:**

**Use your logbook to track how you are using your aroma inhaler and how you are feeling**

1. Use a new page of the logbook for each of the seven days of the study
2. If you forget or purposely do not do the aroma inhaler, please make a note with a brief reason why
3. Do not stop the study because you miss a step of using the inhaler or recording in the logbook
4. Keep your logbook in a secure place as we will collect it at the end of the study
5. Do not write important or private information that does not have to do with using your aroma inhaler in this logbook
6. Do not write your name on the logbook
7. All information provided in the logbook will be kept confidential
8. **Return within 3 days of completion**

**\*NOTE:** If you develop any uncomfortable symptoms such as a headache, stop using the aroma inhaler, recap, and retry a little later. If unpleasant symptoms continue the next time, discontinue use and contact [name], the Principal Investigator (PI), at [[contact]](mailto:[contact]).

Day 1

Please indicate each time you use your inhaler today (approximate time of day)

- I used my aroma inhaler as directed for the first time today
- I used my aroma inhaler as directed for the second time today
- I used my aroma inhaler as directed for the third time today

Any additional comments:

If you used your aroma inhaler any extra times, please indicate when and brief reason why  
(example: 2:30p, feeling stressed, and it seemed to help)

One time at the end of each day, after using the inhaler throughout your day, place an X on the line under "I feel as comfortable as possible today"

I feel as comfortable as possible today

Strongly disagree	Strongly agree
<hr/>	

Comments:

If you have any questions or comments, contact [name] at [[contact]](mailto:[contact]).  
Thank you

Day 2

Please place a check mark or X on the line each time you use your inhaler today

- I used my aroma inhaler as directed for the first time today
- I used my aroma inhaler as directed for the second time today
- I used my aroma inhaler as directed for the third time today

Comments: (example: I used my aroma inhaler an extra time today because...)

One time each day place an X on the line under "I feel as comfortable as possible today"

I feel as comfortable as possible today

Strongly disagree	Strongly agree
<hr/>	

Comments:

If you have any questions or comments, contact [name] at [[contact]](mailto:[contact]).

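### Only the intervention arm is listed as keeping the manufacturer's benefit claims, and only its Day 1 logbook page models a benefit: an avoidable push, of unknown size, on unblinded self-ratings

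*Combined protocol and SAP*

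**What the plan says.** Under Documents to Leave in Participant Packet, the INTERVENTION list puts the "Aethereo®Stick information sheet" in the left pocket. The CONTROL list has only the welcome letter and a consent copy in that pocket. The control participant's inhaler is "kept in a secure location until they complete the study", although "It will have been opened and demonstrated with the participant during study introduction".

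The sheet is reproduced in Appendix B. Its opening line describes the sticks as effective and speaks of aromatherapeutic benefits. It adds that "AethereoSticks are widely used in hospitals for adjunctive symptom management and general well-being", and further down that "These precious plant materials can help with symptom relief and help to create a healing environment".

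In Appendix D, the Day 1 page of the intervention logbook invites a note on any extra use and supplies a model: "example: 2:30p, feeling stressed, and it seemed to help". On Days 2 to 7 the prompt is an unfinished sentence that leaves the reason open and states no result. The control logbook has a comfort line and blank comment space each day, with no example.

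The Benefits section takes a neutral position: "The participant may or may not directly benefit from participating in this research".

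**The concern.** Comfort, ease and stress are all self-rated, before and after the week (Study Design). The available text describes neither a placebo inhaler nor blinding, and the logbooks are headed with the group name. Hypotheses 1a and 1b predict higher comfort and ease and lower stress with the inhaler. Written benefit claims that one arm holds during the treatment week can move its ratings in exactly those directions. The Day 1 example pairs use of the product with relief of stress, which is one of the measured constructs, and it stands on the page where that day's comfort is rated.

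Any such movement after baseline falls into the between-arm contrast and cannot be told apart from an effect of bergamot. The Statistical Analysis Plan has no step that addresses expectation. Inability to blind is a reason to keep written materials as neutral and as equal between arms as possible.

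**Working it through.** **Materials side by side**

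| Item | Intervention | Control |
|---|---|---|
| Manufacturer's sheet kept for the week | Listed | Not listed |
| Sheet in the unopened packet (Contents of Study Packets, item 2, not split by arm) | Yes | Apparently yes |
| Logbook example, Day 1 | Benefit stated | None |
| Logbook example, Days 2-7 | Neutral | None |
| Reminder paper (directions for use, no benefit claim) | Listed | Listed |

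The asymmetry in what is kept is therefore on the page. It is not complete in what is seen: packets are opened and reviewed with each participant (Study Packet is Opened, step 6), although the list at that step does not mention the sheet.

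**The plan's own figure.** Inputs from Sample Size: f = 0.25, alpha = 0.05, power 80%, 2 groups, m = 2 measurements, correlation r = 0.50. The test has 1 and N - 2 degrees of freedom.
- Between-group effect: λ = f² × N × m / (1 + (m - 1)r) = 0.0625 × 98 × 2 / 1.5 = 8.17, power 0.808. The smallest even N reaching 80% is 98, so the stated figure reproduces.
- Group-by-time interaction: λ = f² × N × m / (1 - r) = 0.25N. This needs only N = 34 (λ = 8.5, power 0.807) and does not reproduce 98.

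The sample size is thus consistent with the between-group effect, while the Statistical Analysis Plan names repeated measures ANOVA without saying which term tests the hypotheses. Both are shown below.

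**Scale of a pure expectation shift.** Assume no true effect and a shift of b SD in the intervention arm's post-score only, equal SDs at both times, r = 0.5 and 49 per arm. The documents give no value for b; 0.1 to 0.2 is an assumption for illustration.
- Group-by-time: SD of change = √(2(1 - 0.5)) = 1; standard error = √(2/49) = 0.202; λ = b² × 49/2.
- Between-group effect: the average of the two measurements moves by b/2 and has SD √((1 + 0.5)/2) = 0.866; λ = ((b/2)/0.866)² × 49/2.

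| b (assumed) | Group-by-time λ | Rejection rate | Between-group λ | Rejection rate |
|---|---|---|---|---|
| 0 | 0 | 0.050 | 0 | 0.050 |
| 0.1 | 0.245 | 0.078 | 0.082 | 0.059 |
| 0.2 | 0.980 | 0.165 | 0.327 | 0.087 |

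These are rates for a single outcome.

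**The case against.** The strongest reply is that the bias belongs to the design. One arm has an inhaler and the other has none, everyone knows which, and removing a sheet and a phrase leaves that intact. This stands: the materials add only an increment, the documents give no way to measure it, and the study is a pilot with feasibility aims. It does not make the increment worth keeping, since it can be avoided without touching the design.

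Several stronger readings are tempting, and the documents do not support them.
- A reader might infer that the intervention arm is told in writing that bergamot reduces stress. The visible sheet is generic: it covers a range of oils and blends and names neither bergamot nor stress.
- A reader might infer a contradiction with the Benefits section. Saying that materials can help is more favourable in tone than saying participants may or may not benefit, but it does not contradict it.
- A reader might infer that controls never see the claims. They may, briefly, when the packet is opened. Moreover, the amendment in Appendix G has materials mailed rather than handed over, so who holds which paper under that procedure is not established.
- A reader might infer that the logbook coaches benefit all week, or that biased reasons for extra use distort a planned result. The example appears once, and the plan takes adherence from the logbooks but specifies no analysis of those reasons.

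The welcome letter and consent pages are not in the public text, so any balancing wording there cannot be checked.

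**Conclusion.** The point holds as a modest one. By the packet lists, only the intervention arm keeps material claiming benefit, and only its logbook, on one page of seven, models a favourable entry. With self-rated outcomes and no blinding described, this pushes in the hypothesised direction on top of the expectation bias the open design already carries.

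Its separate size is unknown. The rejection rates of about 8-17% (group-by-time) and 6-9% (between-group) show only what an assumed 0.1-0.2 SD shift would do with 49 per arm and r = 0.5. They should not be read as this trial's false-positive rate or as an estimate of what these materials cause. The case for change rests on the low cost of removing an avoidable asymmetry.

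**What to change.** 1. Delete the "Aethereo®Stick Information Sheet" from Contents of Study Packets (item 2) and from the INTERVENTION list (left pocket, item b). Directions for use, storage and what to do about reactions are already in the intervention logbook and on the reminder paper.
2. Replace the Day 1 example with the neutral prompt already printed on Days 2 to 7.
3. Acknowledge the open-label, self-report limitation when Aim 1 is interpreted. The first two changes do not remove it.

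The cost is a minor IRB amendment and the loss of the sheet's product-life and clip text. The product-life text matters little over seven days, given the roughly three months the sheet quotes for an opened stick. Separately, the sheet's description of the breathing technique differs from the logbook's. Since adherence to the intervention protocol is to be calculated from the logbooks, the sponsor should reconcile those passages whatever is decided about the sheet.
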